Many chemotherapeutic agents compromise the integrity of the mucosal barrier in the gut, allowing translocation of gram-positive bacteria in secondary lymphoid organs. While this has, until recently, been considered an undesirable side-effect, it may also represent one mechanism by which chemotherapy stimulates an effective anti-cancer immune response. It has been proposed that the priming of Th17 T-cell responses against commensal microbes following disturbance of the gut mucosal barrier facilitates the accumulation of Th1 helper T cells at the site of the tumor, and thus contributes to tumor regression. Gut microbes may also contribute to the efficacy of chemotherapeutic agents through metabolism of the chemotherapeutic agent to its active form. We will test the hypothesis that gut microbial composition can influence immune response to the tumor, resulting in inter-individual differences in the response to anti-cancer therapies. We will also explore how host factors and microenvironmental factors influence the local immune response to the tumor.

We propose the following specific aims:

- 1. To demonstrate feasibility and acceptability of protocol procedures and measures, including in-home collection of a fecal sample, collection of a blood sample by venipuncture, and collection of breast tissue from newly diagnosed breast cancer patients prior to initiation of neoadjuvant breast cancer therapy.
- 2. To estimate rates of gastrointestinal side effects and pathological complete response in women with breast cancer treated with neoadjuvant chemotherapies, by breast cancer subtypes, tumor characteristics, cancer treatment, and by categorical measures of gut microbial composition, diversity, and metabolic activity.
- 3. To estimate the associations of pre-treatment gut microbial composition, diversity, and metabolic activity with anticancer immune responses, measured as relative abundance of immune infiltrates in pre-treatment FFPE breast tumor tissues, and as relative abundance of circulating lymphocytic subtypes (Th1, Th2, Th17, and Treg) in blood samples collected prior to initiation and following completion of neoadjuvant

IRB # 204897 Site: UAMS Version 5 06/07/2019

chemotherapy.

4. To estimate associations of local and systemic immune responses with host factors such as age, BMI, and smoking status, and with measures of the breast microenvironment including mammographic density and benign parenchymal enhancement on breast MRI.

Study Population

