We anticipate identification of 60 eligible women among patients diagnosed with breast cancer at UAMS and recommended for neoadjuvant therapy over the course of a year and estimate that, of these, 40 will consent to participate and complete study assessments.

Potentially eligible participants will be identified by their treating oncologist in the Medical Oncology Clinic. The study will be presented to potential participants prior to initiation of chemotherapy. We will allow the patient as much time as she needs to think about participation, and discuss her concerns with friends, relatives, and professional staff before making a decision.

Written consent will be requested from patients who meet eligibility criteria. The informed consent process will be conducted by study staff. We will not advertise for study participants. No compensation will be provided to study participants.

Inclusion Criteria

Eligible participants are women aged 18 years or older, who are:

- Diagnosed with invasive breast cancer and prescribed a regimen that includes neoadjuvant therapy prior to breast surgery.
- Able to provide informed consent.

Exclusion Criteria

- History of any previous malignancy, other than non-melanoma skin cancers
- Inability to tolerate phlebotomy
- Immunosuppressive therapy for any other condition
- Fever or active uncontrolled infection in the last 4 weeks
- Inflammatory bowel disease
- Surgery of the stomach, small or large intestines, appendectomy, gastric bypass or gastric banding in the past 6 months.
- Active autoimmune disease, including, but not limited to, SLE, MS, ankylosing spondylitis

Study Design

We propose a small longitudinal study to demonstrate the feasibility of measuring the gut microbiome and immune infiltrates in pre-treatment tumor tissue from newly diagnosed breast cancer patients who will subsequently undergo neoadjuvant therapies. This study will provide preliminary data in support of a proposal for an outcomes study of the roles of the gut microbiome in response to cancer therapies.

IRB # 204897 Site: UAMS Version 5 06/07/2019

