This protocol involves the collection of three types of biospecimens from each participant. These collections would occur as follows: fecal samples will be collected prior to, and following completion of neoadjuvant chemotherapy by the participant, in her home, using a standard collection kit; venipuncture-collected blood samples will be collected prior to, and following completion of neoadjuvant chemotherapy. In addition, we will retrieve archival breast tissue samples, if available, from a clinically-indicated pre-treatment biopsy. Participants will be asked to complete a baseline questionnaire which includes items querying demographic and lifestyle factors and medical history which may be related to breast health and disease prognosis. Participants will be asked to complete FACT-G7 (Quality of life) questionnaire and a questionnaire on gastrointestinal side effects while at routine chemotherapy-related visits.

All study procedures are considered to be of minimal risk.

Assessment	Screening	Baseline (prior to chemo)	Interim (during chemo at the time of routine visits)	Prior to Surgery	After Surgery
Informed consent	Х				
Eligibility	Х				
Archival tumor tissue from pre- treatment biopsy for IHC		lf available			
Data from clinically indicated CBC with diff		lf available			
In home collection of fecal sample		Х		Х	
Study blood sample (<30mL)		Х		Х	
General questionnaire (demographic information, health history and lifestyle)		X			
Pretreatment mammographic evaluations and breast MRI		lf available			
FACT-G7 (Health-related quality of life)		Х	Every 2 weeks		
Gastrointestinal symptom checklist			Every 2 weeks		
Assessment of pathologic complete response during routine clinical care					X

Schedule of Study Events

IRB # 204897 Site: UAMS Version 5 06/07/2019

Outcome definition

The study outcome would be assessed at the time of surgery. Complete pathologic response will be defined as the absence of any residual invasive cancer on hematoxylin and eosin (H&E) evaluation of the resected breast specimen and all sampled ipsilateral lymph nodes following completion of neoadjuvant systemic therapy (ypT0 ypN0 in the current AJCC staging system).

Microbial DNA assays

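### The gastrointestinal checklist has no baseline administration, so the plan describes no way to separate pre-existing symptoms from treatment-emergent ones under Aim 2

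*Combined protocol and SAP*

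**What the plan says.** In the combined protocol and SAP, Aim 2 under Specific Aims reads "To estimate rates of gastrointestinal side effects and pathological complete response", broken down by tumor subtype and characteristics, treatment and categories of gut microbial measures. The Data Analysis section restates Aim 2 in terms of pCR only, with reported gastrointestinal symptoms among the grouping factors.

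The Study Design section says participants will complete FACT-G7 and "a questionnaire on gastrointestinal side effects while at routine chemotherapy-related visits". In the Schedule of Study Events:

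- The row "FACT-G7 (Health-related quality of life" is marked at Baseline and every 2 weeks in the interim period.
- The row "Gastrointestinal symptom checklist" is marked every 2 weeks in the interim period and nowhere else. Its Baseline cell is empty.
- The interim column is headed "Interim (during chemo at the time of routine visits", so it is not a pre-treatment assessment.

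The general questionnaire at Baseline is described as covering "items querying demographic and lifestyle factors and medical history which may be related to breast health and disease prognosis". Gastrointestinal symptoms are not named there. The gastrointestinal exclusions are "Inflammatory bowel disease" and gastrointestinal surgery in the past 6 months.

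**The concern.** A side effect is a change brought about by treatment. A form completed only during treatment records whether a symptom is present, not whether it is new. Every woman here receives chemotherapy, so her own pre-treatment state is the only reference available, and the plan does not describe recording it. Women with other long-standing gut symptoms are eligible.

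Three uses of the data are exposed:

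- **The side-effect rate named in Aim 2.** It would absorb symptoms that predate the first dose.
- **The breakdown by microbial category.** Pre-existing gut symptoms are plausibly related to the baseline microbiome, which is the exposure of interest.
- **Symptoms as a factor for pCR.** The Background argues that gastrointestinal toxicity caused by chemotherapy may mark one way in which the treatment works. Symptoms present beforehand do not mark that mechanism.

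The estimates are meant to help plan a larger study, so an error here would carry forward. The protocol insists on pre-dose collection for the fecal and blood samples; the checklist is the exception.

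**Working it through.** The plan states no rate, precision or power for gastrointestinal side effects, so there is no figure to reproduce. The 47% power in Power and Sample Size concerns the pCR trend across tertiles and does not depend on the checklist.

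**Inputs**

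- From the documents: 40 women expected to complete the study (Study Population); microbial measures grouped in tertiles (Data Analysis), so about 13 women per tertile.
- Assumed, because the documents give no values: baseline symptom prevalence b = 10%, 20% or 30%; treatment-emergent proportion t = 50% overall; t = 35% and 65% in the extreme tertiles.
- Also assumed: every baseline symptom persists and is ticked, and baseline and emergent symptoms are independent.

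**Overall rate.** Observed on-treatment proportion = t + (1 − t) × b. With t = 0.50:

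- b = 0.10: 0.50 + 0.50 × 0.10 = 0.55
- b = 0.20: 0.50 + 0.50 × 0.20 = 0.60
- b = 0.30: 0.50 + 0.50 × 0.30 = 0.65

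Among 40 women, these prevalences mean 4, 8 or 12 with a symptom before treatment.

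**Contrast between tertiles, same b in each.** The true odds ratio is (0.65/0.35) ÷ (0.35/0.65) = 3.45.

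| b | Lower tertile | Upper tertile | Observed odds ratio |
|---|---|---|---|
| 10% | 0.35 + 0.65 × 0.10 = 0.415 | 0.65 + 0.35 × 0.10 = 0.685 | 3.07 |
| 20% | 0.35 + 0.65 × 0.20 = 0.480 | 0.65 + 0.35 × 0.20 = 0.720 | 2.79 |
| 30% | 0.35 + 0.65 × 0.30 = 0.545 | 0.65 + 0.35 × 0.30 = 0.755 | 2.57 |

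**Contrast between tertiles, different b.** The same formula gives both directions of bias:

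- b = 10% in the lower and 30% in the upper tertile: 0.415 against 0.755, odds ratio (0.755/0.245) ÷ (0.415/0.585) = 4.34, above the true 3.45.
- b = 30% in the lower and 10% in the upper tertile: 0.545 against 0.685, odds ratio (0.685/0.315) ÷ (0.545/0.455) = 1.82, below it.
- No true contrast (t = 50% in both), with b = 10% and 30%: 0.55 against 0.65, odds ratio (0.65/0.35) ÷ (0.55/0.45) = 1.52, where the truth is 1.

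**Scale against sampling error.** For an observed 60% with n = 40, the 95% half-width is 1.96 × √(0.60 × 0.40/40) = 0.15. For 35% against 65% with 13 women per tertile, the standard error of the log odds ratio is √[2 × (1/4.55 + 1/8.45)] = 0.82, and the 95% interval around 3.45 is about 0.7 to 17.

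**The case against.** The strongest reply is that the instrument and the counting rule are not in the documents. The Study Design text describes the form in terms of side effects while the schedule calls it a symptom checklist, and such a form may ask about onset, change or attribution. A reader might infer that pre-existing symptoms will be counted as side effects and that the rate is therefore biased upward. The documents do not support that as a fact; they support only that no means of separation is described. An attribution item, if there is one, would still rest on recall after dosing.

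A reader might also infer that the gap cannot be repaired for anyone already enrolled. That goes too far. The baseline questionnaire covers medical history, and the Future research section lists comorbidities and clinical course among the data collected, so partial recovery cannot be ruled out. It would be weaker than the same checklist completed before dosing.

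Further points stand in part:

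- The Study Design sentence alone does not exclude a baseline form. It places FACT-G7 at the same visits, and the table nevertheless gives FACT-G7 at Baseline. The evidence is the empty Baseline cell in the schedule.
- The Data Analysis section specifies no analysis of side-effect rates, so the tertile odds ratios illustrate an analysis that Specific Aims implies but the plan does not set out.
- The study is an exploratory pilot whose defined outcome is pCR, and the assumed bias is smaller than the sampling error at this size. That limits the practical harm. It does not excuse a systematic error that is cheap to avoid and that a larger study would inherit.

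**Conclusion.** The point holds in this form: under the plan as written, pre-existing and treatment-emergent gastrointestinal symptoms cannot be told apart, and the checklist yields on-treatment prevalence. The schedule gap is certain; the size of its effect is not.

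If pre-existing symptoms persist and are ticked, the side-effect rate is overstated, by 5 to 15 percentage points in the illustration. Associations with the microbiome are attenuated if baseline prevalence is equal across tertiles (3.45 falling to between 3.07 and 2.57) and may be biased in either direction if it is not. Apart from the 40 women and the use of tertiles, every input is assumed.

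The pCR outcome itself and its 47% power figure are unaffected. The change is worth making because a named aim depends on it.

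**What to change.** 1. In the Schedule of Study Events, mark the gastrointestinal symptom checklist in the Baseline column, completed with the baseline FACT-G7 before the first dose. Amend the Study Design sentence to match.
2. In Data Analysis, define a gastrointestinal side effect as a symptom that is new or worse than baseline, and add the estimation of side-effect rates on that definition, which the section now omits.
3. Where symptoms are a factor for pCR, use that definition alongside any-symptom prevalence.
4. Report separately the women already dosed without a baseline checklist.

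The cost is one short extra form per woman, at a contact where FACT-G7 and the general questionnaire are already completed, and a minor protocol amendment. The sample size does not change.

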Fecal collection: The first fecal sample should be collected prior to initiation of neoadjuvant therapy; a second fecal collection will be collected after chemotherapy and prior to surgery. In each case, the sample will be collected by the participant at home using an OMNIgene GUT sample collection kit. The samples, labeled with a code and no other patient identifiers, can be brought to the clinic or can be mailed by participants to University of Arkansas for Medical Sciences, Cancer Clinical Trials Office, Re: IRB # 204897, [name]. If mailed, the postage date must be on or before the first day of chemotherapy treatment to be considered eligible to continue. It is vital that the first fecal sample be collected prior to the first dose of chemotherapy. Following receipt, samples will be aliquoted into cryovials and stored in a -80 C freezer in the [name] lab, until the complete batch can be sent to [name], c/o [name] / [name], at the Institute for Genome Sciences, University of Maryland School of Medicine, BioPark - 6th floor, [name]. Samples will be labeled with a unique code and no other identifiers prior to sending to the University of Maryland.

DNA extraction and sequencing: DNA will be extracted from fecal samples at the [name] lab. Microbial 16S rRNA genes will be amplified using indexed primers and sequenced using 454-pyrosequencing, as described in the paper by Fuhrman et al 2013 [29]. The DNA analysis that will be performed will focus on the identification and study of microbes in the sample rather than characterization of human genes.

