Flow cytometry: Leukocytes will be isolated and tagged using monoclonal antibodies directed against CD4, CD8. Following permeabilization, cells will be incubated with anti-FOXP3 mAb (eBioscience, USA). Samples will be analyzed using a FACS Canto flow cytometer (BD Biosciences, USA). Number of events will be acquired in list mode. The FACS Diva software package (BD Biosciences) will be used.

Measures of the breast microenvironment: mammographic density and benign parenchymal enhancement

IRB # 204897 Site: UAMS Version 5 06/07/2019

Available mammographic and MRI-based evaluations carried out at UAMS as a part of the diagnostic process will be reviewed by study investigators. Collected mammographic images would be used for measurement of volumetric mammographic breast density using Volpara software [6]. For each woman, standard views (CC and MLO views) will be reviewed. MRI images will be reviewed by [name] in order to measure benign parenchymal enhancement. In the final dataset, mammographic and MRI-based measures will be stored with the participant's study code.

Withdrawal from the protocol

Subjects may discontinue participation in the research at any time without penalty or loss of benefits to which the subject is otherwise entitled. In the event that the participant is unable to attend study visits or tolerate study assessments, the Principal Investigator reserves the right to terminate the subject's participation without the subject's consent. Data from samples collected prior to withdrawal may be used in data analysis unless the subject provides a written request to the Principal Investigator requesting that data and/or any stored samples be destroyed.

Reporting of protocol modifications, deviations or violations

This study will be reviewed by the UAMS Institutional Review Board (IRB).

Any modifications to the protocol will be submitted to the UAMS IRB for review and approval before any such changes are put into effect. If modifications of the consent form are required, these will also be reviewed and approved by the IRB before the study proceeds. In exceptional circumstances, involving major changes in the protocol, patients already entered into the study may be asked to sign a revised consent form (following IRB approval). However, as this study does not involve patient treatment, and is no more than minimal risk, this last circumstance is not likely.

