The Principal Investigator will carefully monitor study procedures to protect the safety of research subjects, the quality of the data and the integrity of the study. All study subject material will be assigned a unique identifying code or number. Data obtained during the study will be entered into C3PR and OpenClinica located in the UAMS clinical trial management suite. C3PR is a cancer Biomedical Informatics Grid (caBIG®, NCI) application that will keep a list of subjects

IRB # 204897 Site: UAMS Version 5 06/07/2019

enrolled and specific information regarding their enrollment. Data will be entered into OpenClinica through electronic web-based case report forms (CRFs). OpenClinica is a secure open source system for electronic data capture and clinical data management. Data from OpenClinica can be easily extracted for analysis throughout the study.

After informed consent is obtained, the data will be collected, coded with a study ID number, and stored indefinitely.

Data Analysis

Analyses will be conducted according to study aims. As the aims are considered exploratory, P values < 0.05 will be considered statistically significant and no adjustments will be made for multiple comparisons.

Aim 1. To assess the acceptability and feasibility of study procedures.

We will describe numbers and characteristics of women who are 1) screened, 2) eligible, 3) consented, and 4) complete collections for each type of biospecimen. In a brief form which will accompany the fecal sample, we will ask enrolled women specifically about the acceptability of, and logistical difficulties with, the procedures for collection and packaging of the fecal specimen.

Aim 2. To estimate proportions of patients with pathological complete response by host factors, breast cancer subtypes, tumor characteristics, reported gastrointestinal symptoms, and by categorical measures of gut microbial composition, diversity, and metabolic activity.

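### A late mailed baseline stool appears to end a woman's further participation, which would lose her pCR, symptom checklists and second blood draw to analyses that need no stool

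*Combined protocol and SAP*

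**What the plan says.** **The rule.** Under Microbial DNA assays, Fecal collection, the first stool "can be brought to the clinic or can be mailed by participants". For the mailed route only there is a condition: "the postage date must be on or before the first day of chemotherapy treatment to be considered eligible to continue". The next sentence, which applies to either route, gives a timing requirement without a consequence: "It is vital that the first fecal sample be collected prior to the first dose of chemotherapy".

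**Eligibility.** The inclusion list asks for consent capacity and for a woman to be "Diagnosed with invasive breast cancer and prescribed a regimen that includes neoadjuvant therapy prior to breast surgery". Neither the inclusion nor the exclusion list mentions stool.

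**Ending participation.** Withdrawal from the protocol lets the investigator end participation for a woman "unable to attend study visits or tolerate study assessments". Late stool is not named. The same section allows data from samples taken before withdrawal to be analyzed unless she asks in writing for their destruction.

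**Aims that do not need stool, wholly or in part.**
- Aim 1 (Data Analysis) counts women screened, eligible and consented, and those who "complete collections for each type of biospecimen".
- Aim 2 estimates pCR by host factors, subtype and tumor characteristics as well as by microbiome category. In Specific Aims it also covers rates of gastrointestinal side effects.
- Aim 4 is "To estimate associations of local and systemic immune responses with host factors such as age, BMI, and smoking status", and with breast density and MRI enhancement.

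**The concern.** Stool is the exposure for Aim 3 and for the microbiome part of Aim 2. A woman without a valid pre-treatment sample cannot contribute there, and nobody would argue otherwise. The difficulty is that the sentence appears to stop everything else as well. She has consented, may have given baseline blood, and will in any case go on to chemotherapy and surgery.

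Two things are at stake. First, usable outcome data are given up, and the women who lose them are selected on whether they returned a kit on time. Second, the pilot's first aim is feasibility. If the study itself stops collecting from women with late stool, completion of the second blood draw and of the checklists depends on stool return, and the larger study cannot read off what completion would otherwise have been.

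**Working it through.** **1. What is lost and what is kept if the rule ends participation.** This follows the Schedule of Study Events, Outcome definition and the withdrawal section.

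| Item | When obtained | Needed for, without stool | Status after a late stool |
|---|---|---|---|
| Baseline blood | Before chemotherapy | Aims 1, 4 | May be used if already drawn |
| Archived tumor tissue | Requested after consent, if available | Aims 1, 4 | May be used if already obtained; otherwise unclear |
| Symptom checklist | Every 2 weeks during chemotherapy | Aim 2 | Lost from then on |
| Second blood | Before surgery | Aim 1; Aim 4 where it uses this draw | Lost |
| pCR | At surgery | Aim 2, host and tumor factors | Lost unless the study still extracts it |

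The retention clause therefore protects early specimens but cannot recover the last three rows, which arise after she has left.

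**2. The plan's own figures.** The stool rule has no figure attached. The nearest ones are the power statements, and both reproduce.
- Aim 2: 40 women in tertiles of 40/3, pCR 0.20 in the lowest and odds ratio 5.0 for the highest. Taking an odds ratio of √5 for the middle tertile gives pCR 0.200, 0.359 and 0.556. For the Cochran-Armitage trend test with scores 0, 1, 2, T = (40/3)(0.556 − 0.200) = 4.74. The null SD is √(0.371 × 0.629 × 26.67) = 2.50 and the alternative SD is √[(40/3)(0.160 + 0.247)] = 2.33. Power = Φ[(4.74 − 1.96 × 2.50)/2.33] = 47.4% with unrounded values, against 47% stated.
- Aims 3 and 4: 20 women, slope 0.67. Taking this per residual SD, the noncentrality is 0.67 × √20 = 3.00 on 18 degrees of freedom. Power is 80.9%, against 80% stated.

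No stated figure is wrong because of the stool rule. The Aim 2 figure concerns microbiome tertiles, from which women without a baseline stool are absent under either reading.

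**3. Selection bias in overall pCR.** Let f be the share of women who leave over stool and D the difference in pCR between those retained and those who leave. Overall pCR is (1 − f)·p(retained) + f·p(left), so the bias from using retained women only is f × D. Neither input is in the documents. Assumed ranges:
- f = 5%, D = 10 points: 0.05 × 10 = 0.5 points
- f = 20%, D = 20 points: 0.20 × 20 = 4 points
- f = 30%, D = 30 points: 0.30 × 30 = 9 points

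**4. Feasibility of the second blood draw (Aim 1).** Let c be completion among retained women. With retained women as denominator the figure is c. With all consented women it is (1 − f)c. What would have happened without the rule is (1 − f)c + f·d, where d, completion in the women stopped, is never observed and can lie anywhere from 0 to 1. Purely as an illustration, take 50 consented, 40 retained and 38 second draws. The two reported figures are 38/40 = 95% and 38/50 = 76%, and completion without the rule could be anywhere from 38/50 = 76% to 48/50 = 96%. The width of that range is always f. The missing information is created by the rule, so no choice of denominator restores it.

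**The case against.** The strongest reply is that the sentence is unclear and does not amount to a rule of removal. It sits among instructions about samples, it does not say who continues or in what, and it applies to one delivery route. The absence of stool from the eligibility and withdrawal sections can be read as a sign that removal from the study was never meant. This stands as far as it goes. A reader might infer that the protocol removes such a woman from the whole study, but the documents do not say so. Even so, continuing is something a participant does, and nothing limits the consequence to the stool analyses, so staff could well apply it to the woman.

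A reader might also infer that every stool-free result would come only from stool-compliant women. That does not follow. Baseline blood and tissue already obtained may be used, most Aim 4 inputs are baseline or archival, Aim 1 reports the consented count, and no analysis set restricts these aims to women with stool.

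It can further be said that pCR is read in routine care, so it need not be lost. True, but the protocol does not say that it would still be extracted for a woman no longer eligible to continue.

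Finally, requiring a pre-treatment exposure sample is defensible in a pilot for a microbiome study. That justifies excluding her from the microbiome analyses. It gives no reason to stop collecting the rest.

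**Conclusion.** The point holds in limited form. Read naturally, the sentence makes further participation depend on the postmark of a mailed baseline stool. If so applied, pCR, checklists and the second blood draw are lost to analyses in Aims 1, 2 and 4 that need no stool. The eligibility, fecal collection and withdrawal sections do not agree on whether this is a ground for leaving.

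The size cannot be computed. The 0.5 to 9 point range for pCR rests wholly on assumed failure rates and assumed differences. It is tempting to set the ceiling of 50 women against the 40 expected to complete and infer a precision loss of √(47/37) − 1 = 13% for Aim 4 correlations on the Fisher z scale. The documents do not support that. Fifty is an upper limit on enrollment, and 40 is the number expected to consent and complete out of 60 eligible. The calculation would also require that baseline data be discarded and that every woman has every Aim 4 measure, whereas tissue and imaging are collected only where available.

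This is an exploratory pilot, and the matter is a cheap improvement that does not threaten its conclusions.

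**What to change.** 1. **Fecal collection.** State that a late or missing baseline stool, by either delivery route, excludes the woman only from analyses using baseline microbiome measures: Aim 3 and the microbiome part of Aim 2. She stays in the study for blood, tissue, imaging, questionnaires and pCR.
2. **Eligibility and withdrawal sections.** Reconcile both with that sentence, so that it is clear that late stool is not a ground for ending participation.
3. **Data Analysis, Aim 1.** Report late or missing baseline stool as a stool-collection failure, and use all consented women as the denominator for every specimen type.

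The cost is a few sentences, plus one blood draw and checklists at routine visits for a small number of women who add nothing to the microbiome aims. pCR comes from routine care and needs only to be extracted.
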